The purpose of the research project is to utilize a participatory research approach in partnership with three communities to test the effectiveness of an existing intergenerational culturally adapted curriculum. With Native American Research Centers for Health (NARCH) funding, the FL/CP was co-created and pilot tested by CBPR partnerships between the University of New Mexico Center for Participatory Research (UNM-CPR) and three tribal communities, the Pueblo of Jemez, Ramah Navajo and Mescalero Apache. These existing long-term partnerships have co-produced the tribal-specific FL/CP curriculums in Pueblo, Navajo and Apache versions. This CBPR project supports the rigorous testing of the intergenerational Family Listening/ Circle Program as a culturally centered and evidence based prevention program that has produced promising

preliminary data in reducing substance abuse risk factors for elementary school children. This grant will not only aggregate sufficient numbers to test FL/CP effectiveness but also illustrate how an intervention can disseminate and share “evidence- based processes and components” and also integrate understandings from implementation and CBPR science, that culture and community context must be integrated for the intervention to be effective and to generate community ownership. The R01 specific aims over a five year period are as follows:

Aim One:

Rigorously test the effectiveness of the Family Listening/Circle Program (FL/CP), with a comparative longitudinal design within and across three small tribal communities, with 4th graders to prevent substance abuse initiation disparities and to strengthen family well-being. Through a quasi- experimental longitudinal design, we will test effectiveness of the FL/CP prevention program with an intervention group of 4th graders as compared with other 4th graders, both within and across the three tribes. Quantitative pre-, post-, 6- month and 1 year –post measures of substance abuse risk and protective factors will be triangulated with qualitative data, also comparing children and parent responses on psycho- social factors, family communication and cultural connectedness. Process evaluation will assess satisfaction, quality, and fidelity to both core evidence and specific cultural curriculum components.

Aim Two:

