Those whom are ineligible in this study are: those that do not give consent and/or assent to participate; those that do not identify as tribal members of Mescalero Apache, Jemez Pueblo and Ramah Navajo or as the family member of someone that identifies as Mescalero Apache, Jemez Pueblo and Ramah Navajo; children and that are not in the targeted range of fourth grade. The inclusion for the comparison group follows the same criteria, in having a child from the fourth grade and being tribal members, but who decide not to participate in the FL/CP program and are willing to assent/consent to take the pre and post-tests.

6) Number of Subjects (Recruitment Target)

Target number of participants is 12 child participants and at least one parent/guardian in the family for a total of two members from one family, an expected 12 families annually for an overall total of 48 family participants over four years per community. Because of expected drop of 1-3 families (known attrition from our feasibility trials) by end of the twelfth session, we will initially recruit 13-14. Comparison participant numbers will be 12 children and 12 parent/or guardians.

The expected sample size for the families will total 576 participants from Fiscal Years 1, 2, 3, and 4 only (3 data collection waves total). Each wave per year will recruit 12 Program and 12 Comparison families. Based on our multiple pilots with each tribe, we have determined a Family will be represented by at least 1 parent with 1 child; thus our participant totals (program & comparison) are 24 youth and 24 parents per tribe per year (48 participants X 3 tribes X 4 years (data collection waves) = 576). Furthermore, based on previous pilots with each tribe it is anticipated the sample will enroll more females than males at an approximate ratio of 70:30 and the majority of participating parents to be female.

Table 2. Data Collection	FY01 (2014- 2015)		FY02 (2015-2016)		FY03 (2016-2017)		FY04 (2017-2018)		FY05 (2018-2019)	
	Sep 14'	Mar 15'	Sep 14'	Mar 15'	Sep 14'	Mar 15'	Sep 14'	Mar 15'	Sep 14'	Mar 15'
*Wave 1	Pre- Test	Post- Test		1-Yr Follow up						
*Wave2			Pre- Test	Post-Test		1-Yr Follow up				
*Wave3					Pre- Test	Post-Test		1-Yr Follow up		
*Wave4							Pre- Test	Post-Test		1-Yr Follow up

* Each data collection wave (4 Waves totaling 288 families) includes three data collection points (pre, post, and 1 Yr Follow Up) for intervention & comparison families.

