The research team will log onto the secure password protected laptop to provide access for the adult participant to take the self-administered pre-web-based survey instrument. For the child participant, a local TRT or UNM research team member will again log onto the secure password protected laptop to administer the pre-web-based survey instrument by reading aloud each question to the child, who will have the laptop with the web-based survey to record each response directly onto the web-based survey behind a desk-top partition, assuring privacy. Once the adult and child pre- web-based surveys are completed the research team member will sign out of the program and shut down the laptop. The consent forms will be collected and placed in a separate sealed envelope and will be transported to UNM in Albuquerque and placed in a different locked filing cabinet in the same locked office of the PI for three years, after which time they (consent forms) will be destroyed according to university procedures in the destruction of hard copies of research documents.

The administration of the post-survey will be conducted at the completion of the twelve week two-hour sessions of the FL/CP prevention/intervention program, and 1yr later and will follow the same steps taken in the administration of the pre-survey as outlined above for both the adult and child participant.—A comparison between pre/post and one year post survey will be conducted by t-testing of comparisons. Findings with statistical significance will be reported and an executive summary will be included. The research team will utilize a participatory approach and engage the tribal research team in the interpretation of the initial findings. Data will be interpreted by the UNM and Tribal Research Teams to ensure cultural appropriateness and reflection of the lived experience of community partners. Dissemination of findings for each community will be based on recommendation by the tribal research team. Past research experience with other tribal communities recommended the preparation of powerpoint slides with findings and brief executive summaries to be shared with tribal leadership and program staff.

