This R01 therefore: 1) supports multilevel understanding and assessment of the FL/CP prevention effectiveness through a quasi-experimental comparison between intervention and comparison children, with triangulation of quantitative and qualitative impact and process measures, and assessment of both core evidence-based and specific cultural components; 2) strengthens research skills of our tribal colleagues as co-researchers building upon research capacities gained from previous CDC and NARCH funded projects; 3) supports a within-tribe longitudinal (pre-post, 6-month post, and 1-year post) that compares program impacts on 4th grade children, their parents and families; and 4) enables an aggregated sample for testing FL/CP effectiveness with sufficient numbers to achieve statistical significance, given effect sizes for preliminary data; and as a scientific inquiry into the role of CBPR in translational research to reduce disparities in Indian country.

As Cook and Campbell (1979) note, there are a wide variety of factors that make the use of randomization procedures in group designs difficult to impossible, especially in field research settings. In the present case, there are a number of factors at work that make the randomization of participants to either an intervention or usual and customary treatment group not feasible. First, the tribal communities that are participating in the proposed

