project are small and close-knit, characterized by highly interwoven social networks [Cook & Campbell, 1979]. As a result, randomly assigning some children and families to the intervention group and not others is problematic because doing so would likely be socially disruptive. Second, the employment of randomization procedures in this setting implies a level of outside political control that is not achievable in tribal communities. These communities have histories of disadvantage and discrimination, and decisions are usually politically closed to those outside the community, research groups included. Third, the norm of collective equity and CBPR processes which honor tribal voice is prominent and strong, and randomization procedures can mitigate against the ethical responsibility to work towards tribal ownership and sustainability once the grant ends [Buchanan, Miller, & [name], 2007]. We propose therefore the use of a two arm non-equivalent control group design with pretest, immediate post- test, and 12 month follow-up assessment points (see Table 2 below). Among quasi-experimental designs that could be employed, this design carries several advantages over other designs in being able to infer causality [Cook & Campbell, 1979], and we shall follow data analysis procedures recommended by Cook and Campbell concerning this design. One advantage of this design is that it allows for a more meaningful analysis of the impact of the FL/CP intervention by a comparison of the intervention group with the usual and customary comparison group, an advantage not possible with single-group over time designs. Second, the design provides an analysis of diffusion effects (i.e. the potential influence of the intervention on the comparison group over time). Given the tight social networks and small number of interconnected families in the three participating communities, we expect some degree of program diffusion in the comparison group families. We will employ analysis procedures to examine this potential diffusion effect (see below in Aim 3).

Study Personnel – N/A

Location – N/A

Informed Consent – N/A

Procedures – N/A

22) Sharing of Results with Subjects/Incidental Findings

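### The only test named is an unspecified t-test; the promised program-versus-comparison contrast between self-selected groups has no stated estimator, pretest handling or allowance for shared sessions

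*Combined protocol and SAP*

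**What the plan says.** The test is named under the quality assurance plan in Section 14 (Data Management): "A comparison between pre/post and one year post survey will be conducted by t-testing of comparisons". The surveys are a pretest and post-surveys given "at the completion of the twelve week two-hour sessions of the FL/CP prevention/intervention program, and 1yr later". The sentence does not say which groups are compared or how the pretest is used.

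The promised inference is between groups. Aim One (Section 3) tests the program "with an intervention group of 4th graders as compared with other 4th graders, both within and across the three tribes". Section 21 describes a "quasi-experimental comparison between intervention and comparison children" and justifies the two-arm, non-equivalent design by a "comparison of the intervention group with the usual and customary comparison group, an advantage not possible with single-group over time designs". For the analysis of that design it says "we shall follow data analysis procedures" recommended in a cited methods text, and names no procedure. It also says "we expect some degree of program diffusion in the comparison group families" and points to diffusion procedures under Aim 3, which do not follow in the supplied text.

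The groups are self-selected. Section 5 defines comparison families as eligible families "but who decide not to participate in the FL/CP program and are willing to assent/consent to take the pre and post-tests". Section 7 adds those not selected, and fills program places in order of enrolment. Sections 10 and 11(e) describe program families meeting as one group of 12. Section 16 refers to an intent-to-treat design, but only for the continued assessment of families who stop attending.

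**The concern.** The t-test sentence is ambiguous. It lists survey occasions, which suggests tests of change over time. It could also mean tests between groups, because Section 7 uses the word comparisons for the non-program families. Each reading leaves a problem.

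- **Within arm.** Fourth graders change as they grow older. Pretest to one-year follow-up spans about 15 months by Section 14 (twelve weeks plus a year), or about 18 months by the column positions in Table 2. A significant change in the program arm would not separate the program from that drift.
- **Between arms.** A plain t-test treats the children as independent, although program families attend together in groups of 12. If outcomes are correlated within a group, the standard error is too small.

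Under either reading, the handling of the pretest is unstated. It matters here because self-selected arms may differ at the start, and the two usual estimators can then disagree. Section 14 also says that significant findings will be reported, so an unnamed estimator leaves room to choose after the results are seen.

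**Working it through.** **1. The plan's own count.** Section 6: 12 families × 3 tribes × 4 waves = 144 families per arm, 288 in all, and 576 participants at one child and one parent each. This reproduces. Alpha, effect size, SD, pre-post correlation and ICC are not given, so what follows is illustrative. It assumes a two-sided 5% level, outcome SD 1 and pre-post correlation r = 0.5. The SD of change is then √(2(1 − r)) = 1. Attrition and diffusion are not modelled.

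**2. Between-arm change-score t-test ignoring sessions.** Let the ICC apply to change scores in the 12 program groups of 12, with comparison children independent. True standard error ÷ t-test standard error = √((1 + 11·ICC + 1)/2). The false-positive rate is approximately P(|Z| > 1.96 ÷ ratio).

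| Assumed ICC | Ratio | False positives |
|---|---|---|
| 0 | 1.00 | 5.0% |
| 0.02 | 1.05 | 6.3% |
| 0.05 | 1.13 | 8.3% |
| 0.10 | 1.24 | 11.5% |

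Simulation (20,000 trials per setting) gave 5.1%, 6.3%, 8.1% and 11.6%.

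**3. Within-arm paired t-test, no program effect.** With 144 independent children the noncentrality is drift × √144 ÷ 1. For drifts of 0.1, 0.2 and 0.3 SD this is 1.2, 2.4 and 3.6, and the program arm is significant 22%, 66% and 95% of the time. Testing both arms separately does not help. If both truly change by 0.15 SD, each is significant with probability about 0.44, so exactly one is significant with probability 2 × 0.44 × 0.56 = 0.49.

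**4. Pretest handling.** With a baseline gap d between arms and a post-on-pre slope b, difference in change and pretest-adjusted difference disagree by d(1 − b). For d = 0.2 SD and b = 0.3, 0.5 and 0.7, that is 0.14, 0.10 and 0.06 SD. Which one is unbiased depends on whether the gap would have stayed constant or shrunk without the program.

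**5. One option that allows for sessions.** Take the 12 tribe-by-wave differences and test their mean with 11 df. Each difference has SD √((2 + 11·ICC)/12), and noncentrality for a true 0.3 SD effect is 0.3 × √12 ÷ that SD. Power is 64%, about 60%, about 54% and about 46% at ICC 0, 0.02, 0.05 and 0.10. A plain t-test with independent children has noncentrality 0.3 ÷ √(2/144) = 2.55 and power 72%.

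This test holds 5% only if the 12 groups are independent. Tribes have their own curricula and carry trained facilitators from year to year. With an assumed total ICC of 0.05, simulation with random tribe effects gave 5% when all of it is at session level, 9% when half is at tribe level and 13% when all is at tribe level.

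**The case against.** The strongest reply is that the design section settles the matter. Section 21 commits to a between-group comparison, explains why that is better than a single-group design, and adopts procedures meant for non-equivalent groups. The t-test sentence sits in a data-management section, not an analysis section. Section 21 also appears to come from a longer text, since it points to an Aim 3 analysis that does not follow and to a later Table 2 that in fact stands earlier. Fuller analysis wording may exist elsewhere.

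Much of this stands. A reader might infer that the investigators plan only pre/post tests within the program arm, or have abandoned the comparison. The documents do not support that: the between-group contrast is stated more than once, so the within-arm reading is the less likely one. Nor can it be said that the cited procedures fail to deal with baseline differences, because they are not reproduced.

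The gap remains all the same. Adoption by reference names no estimator, covariate or treatment of the pretest, and the one test that is named does not supply them. The attachments listed in Section 12 include no analysis plan.

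It is also fair to say that the numerical case depends on assumptions. With no session correlation, the plain between-arm test has its nominal 5% error, and at an ICC of 0.02 the excess is about one percentage point.

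**Conclusion.** The point holds as an analysis that is promised but not specified. It should be fixed before analysis. As written, the t-test either misses the stated contrast or tests it with a standard error that ignores the shared sessions. The second, likelier reading gives about 6%, 8% and 12% false positives at assumed ICCs of 0.02, 0.05 and 0.10. Those figures need session correlation to be present, which is plausible from the group format but is not quantified in the documents. The within-arm rates show only what would happen if the sentence were carried out that way, and are not a forecast of the plan. Confidence is medium, because the procedures adopted by reference could resolve part of this once written out.

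**What to change.** Replace the t-test sentence in Section 14 and cross-refer it to Section 21. The new paragraph should:

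- For each child and parent outcome, estimate the program-minus-comparison difference at each planned follow-up, using the pretest and adjusting for tribe and wave.
- Use standard errors that allow for the tribe-by-wave program groups. Testing the 12 differences with 11 df is one option, valid only if inference is limited to these three tribes or the effect does not vary by tribe.
- Name one primary estimator before analysis, with its assumption. Difference in change assumes that any baseline gap would have stayed constant without the program. Pretest-adjusted difference assumes that families with equal pretests would have had equal later scores. Report the other as a sensitivity analysis.
- Keep within-arm tests for description only.
- State that neither estimator removes selection-by-maturation (program families changing faster anyway), and that the expected diffusion may shrink the contrast.

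The 6-month measure in Aim One and in the list of R01 purposes in Section 21 should be reconciled with Table 2 and the design statement in Section 21, which omit it. If the procedures adopted by reference already answer these points, write them into the protocol.

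The drafting cost is one paragraph, with no added visits or participants. The cost in precision is real. The standard error rises by 5%, 13% and 24% at assumed ICCs of 0.02, 0.05 and 0.10. If the 12-difference test is chosen, illustrative power at 0.3 SD falls from 72% to 64% even at ICC 0, and to about 46% to 47% at ICC 0.10. The two estimates may also disagree, and the report would have to say so.

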WAVE TOTAL = 12 Program Families (12 families X 3 tribes X 4 waves = 144 families (144 students + 144 parents = 288 participants)

= 12 Comparison Families (12 families X 3 tribes X 4 waves = 144 families (144 students + 144 parents = 288 participants)

7) Recruitment Methods

Members of the tribal research team will work with the schools from each community and will identify the potential participants from the fourth, grades of these schools. Letters will be sent home with the fourth grade children and TRT members; and by TRT members presenting to the children in their classrooms on the Family Listening Program and how interested students may participate in this research project. The attached recruitment letter will have minor changes by TRT members who will insert their contact information specific to each community. (see Attachment A). Should a child express an interest then the research team member will follow-up with the parents of the child and the components of the Family Listening/Circle Program will also be shared.

Based on previous pilots with all tribes, all youth participants will be between 9-10 years of age and be enrolled in 4th grade. Evidence of community support and the ability to recruit participants, implement measurement and protocols, and oversight exists through the previous feasibility trials and earlier grants and collaborative work. . At a minimum, Mescalero has 5 years, Ramah has 11 years and Jemez has 14 years of NIH research funded experience with the UNM Center for Participatory Research; which resulted with this multi-tribal application to test effectiveness. The current partnering opportunity stems largely from feasibility and development efforts, multiple pilot projects, presentations and publications. The Tribal Research Teams (TRTs) themselves, are also direct outcomes of previous Community-Based Participatory Research (CBPR) projects that have elevated Advisory Councils (typical of most CBPR projects) to more action-oriented shared leadership bodies that co-design, co-implement and co- translate findings while providing direct research oversight through tribally-driven research and approval processes, and a multi-tribal/academic partnership connected together by UNM-CPR.

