Child and parent participants and child non-participants. Beginning in YR01 the TRT will begin recruitment, in a manner consonant with the feasibility trials. The TRTs will make informal presentations in 4th grade classrooms and will send home letters of invitation to participate. Letters will be given to all 4th grade students to take home for their parents review. The invitation letter will provide an overview of the FL/CP and invite interested parents and children to learn more. TRT and UNM team members will follow-up with interested parents individually. During the individual information session, potential participants will be told what FL/CP is and involves the primary language of the community (Towa, Apache and Dine languages respectively), or bilingually, with English depending on the preference of the potential participants. After learning about the intervention program, TRT researchers will determine whether the family is willing to participate. Research team members will be prepared to provide informed consent and answer any questions. However, potential participants will be encouraged to take time to weigh the costs and benefits of the program; they can take time to think about it and contact the research team member at a later date. If at a later date they decide to

participate, research team members will arrange a time to meet and perform the informed consent process. FL/CP participant families will be enrolled on a first come first serve basis. The self-selected 4th graders and parents who choose to participate will be drawn from a pool of candidates from several points of risk: the socioeconomic status of the students' families is relatively low, living in areas of poverty, living in rural communities and the majority of students live in single parent households. Those not selected to participate or who decline to participate will be invited to take part in the research study verbally by TRT members (to take pre and 2 post-tests) as non-program participants serving as comparisons. The described recruitment process is the preferred method by the TRTs to date; because it ensures a) involvement with this study is entirely participatory and voluntary and b) an understanding of the research involved by potential participants is obtained and discussed to satisfaction of TRT members, with UNM research team members available as necessary.

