Qualitative data from program manager and leader interviews will be audio recorded and transcribed verbatim. The files will be read through completely then cleaned for filler utterances. The file will then be converted to rich text file document and uploaded into Atlas.ti qualitative software. Coding will occur inductively and a code sheet developed, themes will be developed from codes, then data will be thematically analyzed.

15) Provisions to Monitor the Data to Ensure the Safety of Subjects

For all studies considered greater than minimal risk, include a data and safety monitoring plan (DSMP) for reporting data monitoring committee findings to the HRRC and the sponsor

See attached DMSP report.

16) Withdrawal of Subjects

Taking part in this study is completely voluntary so participants can choose not to participate or withdraw at any time. If participants choose not to participate in the facilitated sessions or become unable to participate (i.e. unable to get off work), we will still seek to obtain all post and one year post assessments (using an intent-to-treat design).

17) Risks to Subjects

A potential risk that may occur during the twelve weekly two-hour sessions of the Family Listening prevention/intervention program in which session six includes a discussion of recognizing types of anger or session eleven on being different, a child or adult may share a troubling experience due to being angry or being different. If needed an individual will be referred to a counselor at the local health clinic. Each tribal community has access to a local tribal behavioral health program at the tribal health clinic. Any costs associated with counseling or other treatment will be the responsibility of the participant. [name], UNM Psychology Professor will also be available as a consultant to the FL/CP facilitators and tribal behavioral health units as a back-up clinical psychologist.

A potential risk to participants is a loss of privacy, confidentiality, and emotional risk. All reasonable efforts to maintain and protect privacy and confidentiality for all participants will be made by the UNM team. University researchers each have multiple years of CBPR research experience ([name], over 25; [name], over 10; and [name], over 14; [name], over nine; [name] over 15), including human subjects and have maintained CITI certification. The likelihood of loss of confidentiality is low, given the UNM research teams experience with research.

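### Intent-to-treat is named, but the only stated analysis is t-tests that leave out families with missing surveys, so bias of unknown size and direction is possible

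*Combined protocol and SAP*

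**What the plan says.** Section 16 (Withdrawal of Subjects) covers participants who stop or cannot attend the sessions: "we will still seek to obtain all post and one year post assessments (using an intent-to-treat design". This is a commitment to collect data. It does not say what happens when a survey is still missing.

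The analysis sentence is in Section 14 (Data Management, Quality assurance plan): "A comparison between pre/post and one year post survey will be conducted by t-testing of comparisons". It does not say whether the tests are paired or two-sample, which families are analysed, or how missing surveys are handled. Section 21 describes a "two arm non-equivalent control group design with pretest, immediate post- test, and 12 month follow-up assessment points" and adds that the analysis will follow a cited text on quasi-experimental methods, without describing those procedures.

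On drop-out, Section 6 says: "Because of expected drop of 1-3 families (known attrition from our feasibility trials) by end of the twelfth session, we will initially recruit 13-14". The totals that follow count "12 Program Families (12 families X 3 tribes X 4 waves = 144 families" and "12 Comparison Families (12 families X 3 tribes X 4 waves = 144 families". No drop-out or over-recruitment figure is given for comparison families. Under Section 7 they come from a different pool: "Those not selected to participate or who decline to participate will be invited to take part in the research study".

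**The concern.** Intent-to-treat needs two things: follow-up regardless of attendance, and an analysis that keeps everyone in the group where they started. Section 16 supplies the first as an aim. The t-tests do not supply the second, because they cannot use a family whose required survey is absent. The pre-to-post, pre-to-one-year and post-to-one-year comparisons may then rest on different families, and the plan would not show it.

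Allocation is already by self-selection, so selective survey loss would add a second source of non-comparability. The trial is meant to support spreading the program as a best practice. A result labelled intent-to-treat that in fact describes the families who returned surveys could mislead that decision.

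**Working it through.** **1. The plan's own counts.** Section 6: 48 participants x 3 tribes x 4 waves = 576, as stated. Families per arm: 12 x 3 x 4 = 144, as stated; both arms, 288.

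**2. Program families enrolled.** There are 3 x 4 = 12 tribe-waves. Recruiting 13-14 in each gives 13 x 12 = 156 to 14 x 12 = 168. The stated total of 144 therefore omits 12 to 24 enrolled program families. Section 29 places the adult pre-test straight after signed consent, so these families should have baseline data.

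**3. Session drop-out.** Lowest 1/14 = 7.1%; highest 3/13 = 23.1%. Families still attending: (13 - 3) x 12 = 120 to (14 - 1) x 12 = 156.

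**4. What a t-test leaves out.**
- Paired or change-score test: any family missing either of the two surveys.
- Two-sample test at post or one year: any family missing that survey.

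The text does not say which is meant. The wording compares occasions, and Section 25 provides linked IDs for the longitudinal surveys, so a paired test is the more natural reading. A family with no post survey is left out of a pre-to-post comparison under either form.

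**5. Possible size, program arm only.** Assume the comparison arm loses no surveys and no drop-out is surveyed. Let d be the drop-out share and f the drop-outs' benefit as a fraction of the retained families' benefit. Then

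observed effect / all-enrolled effect = 1 / [(1 - d) + d x f].

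| f (assumed) | d = 1/14 | d = 3/13 |
|---|---|---|
| 0 | +7.7% | +30.0% |
| 0.5 | +3.7% | +13.0% |
| 1 | 0% | 0% |
| 1.25 | -1.8% | -5.5% |

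For illustration, take a retained-family effect of 0.30 SD (assumed) and f = 0. The all-enrolled effect is 0.30 x 13/14 = 0.279 SD or 0.30 x 10/13 = 0.231 SD, while the t-test shows 0.30 SD. If all drop-outs are surveyed, the overstatement is 0%.

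**6. Direction, both arms.** Bias = dP x gP - dC x gC. Here dP and dC are the survey-loss shares in the program and comparison arms, and gP and gC are the gaps, retained minus missing mean, in each. Assume a gap of 0.5 SD and loss of 1/14 to 3/13:
- gap in the program arm, no comparison loss: +0.036 to +0.115 SD;
- equal loss and equal gap in both arms: 0;
- gap reversed in the program arm, no comparison loss: -0.036 to -0.115 SD;
- equal loss, gap in the comparison arm only: -0.036 to -0.115 SD.

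The documents give neither dC nor either gap, and they give session drop-out rather than dP. They fix neither sign nor size.

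**7. What a better model would recover.** In the f = 0 illustration, a likelihood-based model would still return about 0.30 SD unless baseline predicts who is lost, because a family with only a pre-test says almost nothing about change. Giving those families the comparison arm's average change sets their effect to zero and returns 0.279 or 0.231 SD, the all-enrolled values in that scenario.

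**The case against.** A reader might infer that the plan discards program drop-outs and so overstates the effect by 8-30%. The documents do not support that, for four reasons.

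- Section 16 addresses these families directly and intends to survey them. Only those who also miss a survey are lost, and their number is not given. The 7-23% is session drop-out.
- Nothing says that drop-outs change less. The one reason given as an example is being unable to leave work. Comparison families have no sessions to leave, but those who declined the program or were not selected could return fewer surveys too.
- The top figure pairs the largest drop with the smallest recruitment. If the aim of keeping 12 is met, drop-out is 1/13 = 7.7% to 2/14 = 14.3%, and the extreme case gives 13/12 - 1 = 8.3% to 14/12 - 1 = 16.7%. Even so, a loss of 3 families is within the plan's stated range.
- Deletion of every family missing either survey holds only for paired tests, and the form of test is unstated.

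These points stand, and they limit the finding to a bias of unknown size and direction. The reference in Section 21 to outside procedures is also a real commitment, but it is not described and does not settle the handling of missing surveys. None of this supplies an analysis set or a missing-survey rule, and no form of t-test can use a survey that was never completed.

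**Conclusion.** The concern holds in limited form. The plan names intent-to-treat, but its only stated quantitative analysis leaves out families without the needed survey, and different comparisons may use different families. With no survey-loss rate for either arm, the resulting bias cannot be sized or signed.

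Overstatement is possible if unsurveyed program drop-outs benefited less. The 7.7-30.0% range is a bound under three assumptions: none surveyed, none benefiting, no comparison loss. It is not an estimate. The same arithmetic gives 0% if all are surveyed, and understatement if those lost had done better than those kept. Confidence is medium, because the form of the t-test and the extent of survey loss are both unknown.

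**What to change.** In Section 14, replace the occasion-by-occasion t-tests for Aim One with one likelihood-based repeated-measures model. Pre, post and one-year scores are the outcomes, with a group-by-time term, a family effect, and tribe and wave as covariates. State that the analysis set is all enrolled, pre-tested families, including all 13-14 program families per tribe and wave, in their starting group.

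This uses partly followed families and no longer needs surveys to be missing completely at random. It does not by itself correct loss related to unobserved outcomes. So add one sensitivity analysis that gives program families with missing surveys the comparison arm's average change, and report survey loss by arm at each occasion.

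The cost is a change of wording and a little more analysis work, with no new data. The sensitivity estimate may be smaller than the main one.
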